3.3 Secondary Feasibility Outcomes

2- Feasibility of applying and keeping the 2 blankets in the trauma bay
3- Feasibility of keeping the 2 blankets in the CT scanner suite
4- Feasibility of keeping the 2 blankets in the ED
5- Feasibility of keeping at least one of the blanket in the OR or IR suite (one can be removed for procedures and re-applied at the end of the intervention)
6- Feasibility of keeping the 2 blankets in PACU (for example one blanket is removed in the OR and reapplied at the end of the procedures and kept in PACU before the patient is transferred to the ICU)
7- Feasibility of keeping the 2 blankets in the ICU up to 8 hours of until patient achieves 37.5 degrees Celsius.
8- Reasons why the blanket was not maintained at each of the next phase of care (CT scanner suite, IR suite, OR, ED, ICU)

3.4 Efficacy Outcomes

9- Increase of temperature from admission up to 8 hours of 1 degree Celsius

3.5 Clinical Outcomes

10- Proportion of adherence to body temperature measurement throughout different phases of care (i.e.: ED, CT scanner suite, OR, IR suite, ICU)
11 -Use of concurrent warming strategies(i.e. fluid warmers, FAWB, etc.) within the first eight hours of blanket application in conjunction with, or replacement of, the Ready-Heat® chemical heating blanket

- 12- Number of units of blood products (red blood cells, plasma, platelets, and fibrinogen concentrate) transfused within 24 hours post arrival to the trauma bay
- 13- Coagulation (platelet count, INR, fibrinogen level) and perfusion parameters (pH, base deficit, serum lactate) measured on arrival, and at the next time points collected as per clinician discretion
- 14- Hemoglobin level measured on arrival, and at the next time points collected as per clinician discretion

3.6 Safety Outcomes:

- 15 - Number of times blanket is placed directly on the patient skin
- 16 - Number of times patients developed redness and/or skin burns

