STUDY OUTCOMES	
Primary outcomes (feasibility):
 
 (1) Feasibility of performing a pilot pragmatic randomized controlled trial (RCT) to evaluate effectiveness of the Ready-Heat® blanket to increase temperature by at least 1°C at eight hours from time of blanket placement in the trauma bay in severely injured trauma patients to whom a massive hemorrhage protocol is activated (2) Feasibility of adherence to the application of the Ready-Heat® blanket in patients enrolled in the intervention arm throughout the trauma bay resuscitation; (3) Feasibility of adherence to body temperature measurement throughout the different phases of care (i.e.: TB, ED, CT scanner suite, OR, IR suite, ICU) within the first eight hours of blanket application. (4) Feasibility of maintenance of at least one blanket applied throughout the different phases of care (i.e.: TB, ED, CT scanner suite, OR, IR suite, ICU) 
Secondary Measures:
 
 (1) Concurrent warming strategies used (i.e.: fluid warmers, FAWB, etc.) within the first eight hours of blanket application in conjunction with or replacement of Ready-Heat® chemical heating blanket; (2) Number of units of blood products (plasma, red blood cells, platelets, fibrinogen concentrate) transfused within 24 hours of trauma bay arrival; (3) Coagulation (platelet count, INR, fibrinogen) and perfusion parameters (pH, base deficit, serum lactate) measured on arrival, and at the next time points collected as per clinician discretion; (4) Hemoglobin level measured on arrival, and at the next time points collected as per clinician discretion. 
Secondary Safety Measures:
 
 (1) Number of times blanket is placed directly on the skin; (2) Skin redness and/or burns.
STATISTICAL ANALYSIS	
The results of this pilot trial will be used to assess the feasibility and inform the design of a definitive trial. We will present point estimates of feasibility outcomes with 95% confidence intervals.
 
Demographic and clinical characteristics will be summarized in total and by two arms using mean, standard deviation (SD), median (interquartiles) and range for continuous variables, and percentages for categorical

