5.2.1 Inclusion Criteria

1. Age \geq 16 years
2. MHP activated in the trauma bay (see Table 1)
3. Between 08:00-20:00hrs on weekdays

Table 1 MHP Activation Criteria

MHP activation criteria

• Life-threatening bleeding situation requiring mobilization of blood bank, laboratory and clinical resources.• Anticipated need for at least 4 units of red blood cells immediately and component therapy (platelets, plasma, and fibrinogen).

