5.2.2 Exclusion Criteria

1. Transferred from another healthcare facility
2. Death in the trauma bay prior to randomization
3. Arrival to trauma bay with ongoing CPR
4. Patients with penetrating head injury with Glasgow Coma Scale of 3 AND loss of brain matter through the wound

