5.4.1 Study Visits

The following information will be collected during study visits either in person or remotely reviewing electronic health records. During weekdays, 8 am to 8 pm, the research assistant will be following the patient across the different phases/locations of care and will be collecting data at the same time. Research assistants will access all documented data on the next weekday. Visits and specific data collection are detailed as follows:

5.4.1.1 Visit 1

On admission to the trauma bay: Demographics, injury characteristics and surgical management:

1. Date of injury
2. Time of injury
3. Sex
4. Age
5. Types of surgical procedures performed in the first 8 hours following hospital arrival
6. Date of arrival
7. Time of arrival
8. Time of randomization
9. Name of attending TTL and sub-TTL (if applicable)
10. Initial temperature recorded
11. Was the blanket placed on the patient? Yes/No
12. Time that the blanket was placed on the patient, if registered
13. Reason why blanket was not applied
14. Blanket applied directly to the patient's skin? Yes/No
15. Use of fluid warmers
16. Use of FAWB

5.4.1.2 Visit 2

Within the first eight hours of blanket application:

1. Location of the patient
2. Is the blanket kept on the patient? (Yes/No)
3. If not, what was the reason it was removed?
4. Temperature recorded, hourly (Yes/No)
5. If yes, the temperature recorded
6. Type of temperature measurement
7. Blanket applied directly to patient's skin? Yes/No
8. Use of FAWB
9. Use of fluid warmers

At discretion of the clinician, within the first eight hours of blanket application:

10. Coagulation (platelet count, INR, fibrinogen)
11. Perfusion parameters (pH, base deficit, serum lactate)
12. Hemoglobin

13. Number of units of red blood cells, plasma, platelets, and fibrinogen concentrate administered within the first 8 hours

5.4.1.3 Visit 3

At 24 hours post blanket application:

1. Number of units of red blood cells, plasma, platelets, and fibrinogen concentrate administered within the first 24 hours
2. Type of injury (blunt/penetrating)
3. Injury Severity Score (ISS)
4. Frequency of safety events with skin

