8.1.2 Expected adverse events with Ready-Heat® blankets

Prolonged direct skin contact with the Ready-Heat blanket has been known to cause mild burns. The manufacturer specifies the need for careful supervision when used with “the elderly....people with sensitive skin and those who can't feel heat or regulate heat”¹³. Given that some of the enrolled patients may be sedated due to clinical condition, the study products will be applied with the express direction to avoid direct skin contact. The recommendation will be made to use a standard blanket as an intermediary between the skin and the study product.

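### No skin condition is recorded on arrival or at blanket removal, so the redness/burn outcome cannot reliably separate arrival injuries from those that developed under the blanket

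*Combined protocol and SAP*

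**What the plan says.** Section 3.6 lists outcome 16 as "Number of times patients developed redness and/or skin burns". The protocol summary gives the safety measures as "Number of times blanket is placed directly on the skin; (2) Skin redness and/or burns". Neither place gives a definition, grade, body site or reference time, or says whether the unit is the patient or the event.

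Section 8.1.2 names the harm that the outcome is meant to catch: "Prolonged direct skin contact with the Ready-Heat blanket has been known to cause mild burns".

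Section 5.4.1 sets out what is collected:

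- **Visit 1** (arrival, 16 items): item 14 asks whether the blanket lies directly on the skin.
- **Visit 2** (first eight hours, 13 items): item 7 repeats that question, and item 3 asks why a blanket is no longer on the patient.
- **Visit 3** (24 hours, 4 items): item 4 is "Frequency of safety events with skin".

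The adverse event (AE) rules are in section 8. Section 8.1.1 limits AEs to new events that the investigator thinks may be due to enrolment or the assigned arm, and sends only related ones to the eCRF, with CTCAE coding. Section 8.2.5 asks for AE enquiry at every contact and exempts pre-existing conditions that were noted at screening or baseline, unless they worsen. Section 7.2 summarizes the safety measures descriptively, in total and by arm.

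**The concern.** The trial enrols patients with major trauma and life-threatening bleeding. Some may arrive with abrasions, bruising or burns where a blanket will lie. An outcome that counts what patients developed needs a starting state to compare with, and the schedule does not plan one. It also plans no skin reading when the blanket comes off, which is when mild redness from the device would be easiest to see.

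Skin injury is the one harm that the plan names as expected from this device, and the pilot is meant to inform a definitive trial. If a mark seen later cannot be placed before or after application, the count can err in either direction: an arrival injury may be charged to the blanket, or a device injury may be put down to the trauma.

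**Working it through.** No figure in the plan is disputed, so the check is mainly a comparison of what the outcome needs with what the schedule collects.

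**1. Item count (section 5.4.1).**

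| Visit | Items | Record skin condition or skin events | Record blanket-to-skin contact |
|---|---|---|---|
| 1, arrival | 16 | 0 | 1 (item 14) |
| 2, first 8 h | 13 | 0 | 1 (item 7) |
| 3, 24 h | 4 | 1 (item 4, a frequency) | 0 |

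Over Visits 1 and 2, 0 of 16 + 13 = 29 items describe the skin. The contact items record exposure. The reason-for-removal item records handling; it may catch a reaction that led to early removal, but not redness found at the planned removal.

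**2. Do the AE rules supply the missing baseline?**

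- The exemption in section 8.2.5 applies only to conditions noted at screening or baseline, and the schedule plans no such note for skin.
- Two defaults then pull in opposite directions. Section 8.2.1 treats an event of uncertain cause as related. Section 8.2.5 lets the investigator leave out events that are common in this population. Without a baseline record, the same mark can be counted under one rule or dropped under the other.
- The definition in section 8.1.1 requires an event that may endanger the patient. Mild redness belongs to outcome 16 but may not meet that test.

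**3. Who is present at removal?** In-person follow-up runs from 08:00 to 20:00 on weekdays. A blanket applied after 20:00 − 8 h = 12:00 reaches its planned removal after staffed hours. That is 8 of the 12 enrolment hours (a share of hours, not of patients). Later data come from the chart on the next weekday, and no chart item on skin at removal is planned.

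**4. Does the by-arm summary make a baseline unnecessary?** Randomization balances arrival injuries on average. The documents give neither an arrival rate *b* nor a device rate *d*, so both are assumed here, in the limiting case where every arrival injury is counted. The expected intervention proportion is p = b + (1 − b)d. The 95% half-width of the difference between arms is 1.96 × √{[p(1 − p) + b(1 − b)]/37}.

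- With b = 0.10 and d = 0.05: p = 0.10 + 0.90 × 0.05 = 0.145. Expected counts are 37 × 0.10 = 3.7 (control) and 37 × 0.145 = 5.4 (intervention). The difference is 4.5 points, with a half-width of about 15 points.
- Over b = 5–30% and d = 5–10%, the difference is 3.5 to 9.5 points and the half-width about 12 to 21 points. The half-width exceeds the difference throughout.

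This shows only that the comparison between arms is too imprecise to stand in for a baseline reading. It does not estimate how many events would be misclassified.

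**5. What a clean count would allow.** If arrival injuries are set aside and no new event is seen, the one-sided 95% upper bound on the device rate is 1 − 0.05^(1/37) = 7.8% with 37 patients, or 1 − 0.05^(1/29) = 9.8% with 29. Those are modest statements, but they can be interpreted.

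**The case against.** The strongest reply is that the plan already has several routes to the answer. Outcome 16 refers to what patients developed. AEs must be new and assessed for relatedness. Staff must enquire at each contact, by examination where appropriate. A research assistant follows the patient during staffed hours. Hospital records are source documents (section 13.2), so arrival injuries can often be found later. The summary is by randomized arm. The outcome is secondary and descriptive, and no criterion in section 6.1 depends on it. The CRF itself is not reproduced, so a skin field there cannot be ruled out.

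Much of this stands. A reader might infer that skin is first looked at 24 hours after application. The documents do not support that: AE enquiry starts earlier, and the Visit 3 item may be a running tally. Nor is the outcome wholly unable to separate the two kinds of injury, since charting and the new-event rule will resolve some cases.

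A reader might also infer that the eligibility list contradicts section 8.1.2, because none of the exclusions concerns skin or heat sensation. It does not. The quoted caution names "people with sensitive skin and those who can't feel heat or regulate heat" but asks for careful supervision and does not bar these patients. For patients who may be sedated, the plan responds with an intermediary blanket and an instruction to avoid direct contact.

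What the reply does not supply is a planned reading at either end. The routes it names depend on incidental charting and on judgement. Sections 2.2 and 5.1 mention blinded outcome assessors, but sections 5.1, 5.3.1 and 5.3.3.5 say that only the statistician is blinded, and no blinded skin assessment is described.

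**Conclusion.** The point holds in a limited form. As scheduled, outcome 16 cannot reliably separate skin injuries present on arrival from those that developed under the blanket, and transient or mild redness at planned removal may go unrecorded. The size is best stated as the gap itself: no skin-condition item at Visits 1 and 2, and one undefined frequency at Visit 3. A reader might want a number of false device events among the 37 intervention patients. The documents give no arrival rate, and any such number would also assume that every arrival injury is miscounted, so none is offered.

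The conclusion assumes that the list in section 5.4.1 is what will be collected. If the CRF already has a skin field, the protocol need only say so. This is a cheap improvement to a descriptive safety outcome. It does not affect the sample size, the feasibility criteria or the treatment given.

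**What to change.** In both arms:

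- Add to Visit 1: redness, burn or skin injury in the area to be covered, yes/no, with body site. It can be taken from the trauma survey.
- Add the same item to Visit 2, at blanket removal or at 8 hours.
- Define outcome 16 in section 3.6 as redness or a burn that is new or worsened since application. Use the same definition for the skin item at Visit 3, and state whether patients or events are counted.
- In section 7.2, report it by arm with body site and CTCAE grade.

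The Visit 1 item also gives the exemption in section 8.2.5 a record to rest on. The cost is slightly more data entry. It relies on routine examination and changes no treatment, eligibility rule or sample size. It will not make 37 per arm precise, but it will make the counts interpretable.

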6.0 CRITERIA FOR OUTCOME ASSESSMENT

6.1 Primary outcome assessment

1. *Feasibility of Ready-Heat® blanket to increase temperature by at least 1°C at eight hours from arrival to the trauma bay in massively bleeding trauma patients.*
If the study intervention is unable to increase body temperature by at least 1°C in 80% of patients at eight hours from arrival, the study as it is currently designed will not be deemed feasible.
2. *Feasibility of adherence to the application of the Ready-Heat® blanket in patients enrolled in the intervention arm throughout the initial trauma bay resuscitation* Failure to apply and maintain the Ready-Heat® blanket in more than 20% of patients enrolled in the intervention arm throughout the initial trauma bay resuscitation, the study will not be deemed feasible.
3. *Feasibility of adherence to body temperature measurement throughout different phases of care within first eight hours of blanket application.*
Failure to measure body temperature throughout different phases of care (i.e.: ED, CT, OR, IR, ICU) within the first eight hours of blanket application in more than 20% of enrolled patients, the study will not be deemed feasible.

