7.2 Final Analysis Plan

Demographic and clinical characteristics will be summarized in total and by two arms using mean, SD, median (interquartiles) and range for continuous variables, and percentages for categorical variables. Wilcoxon rank-sum test, Chi-square test or Fisher exact test will be applied for comparing continuous or categorical variables between two arms, as appropriate. To investigate the primary objective on the feasibility of using the Ready-Heat® chemical heating blanket, the proportion (and 95% CIs) of patients with an increased body temperature by at least 1°C at 8 hours from arrival to the trauma bay will be calculated and compared between two arms using Chi-square or Fisher exact test as appropriate. Line graph (with mean and SD) of body temperature over the first 8 hours of blanket application will be plotted for two treatment arms. To search for significant time trends in two arms on the hourly body

temperature measurements within first 8 hours of blanket application, linear mixed effects repeated model will be performed with both fixed (time in hours, treatment arms, and arms by time interaction) and random (patient) effects. To compare treatment effects on the coagulation parameters (platelet count, INR, fibrinogen level), perfusion parameters (pH, base deficit, serum lactate), and hemoglobin levels measured on arrival and over the first 8 hours, linear mixed effects repeated model will also be performed with both fixed and random effects. Skewness and Kurtosis will be tested on the distribution of coagulation, perfusion and hemoglobin parameters. Natural logarithm transformation will be applied to normalize the distribution if necessary. Descriptive analysis will be summarized in total and by arms for safety measurements (i.e., number of units of blood products transfused, number of times blanket is placed directly on patient skin, and number of times patients developed redness and/or skin burns). All analyses will be conducted using Statistical Analysis Software (SAS version 9.4, Cary, NC) and R package (version 4.3.0). P-value < 0.05 will be considered statistically significant.

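### The skin-safety outcome pools redness with burns and counts occurrences, so the planned summary does not give the proportion of patients burned

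*Combined protocol and SAP*

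**What the plan says.** - **Outcome definition.** Section 3.6 lists outcome 16 as "Number of times patients developed redness and/or skin burns". The protocol summary names the same safety measure as "Skin redness and/or burns", with no unit.
- **Analysis.** Section 7.2 plans descriptive summaries, in total and by arm, of safety measurements that include "number of times blanket is placed directly on patient skin, and number of times patients developed redness and/or skin burns". It does not separate burns from redness, and it plans no proportion of patients affected and no confidence interval for these items. The protocol summary promises 95% intervals for the feasibility outcomes only. Section 7.2 does not mention the adverse event data.
- **Data collection.** The one named skin-event item is at Visit 3 (section 5.4.1.3): "Frequency of safety events with skin". Visit 2 records direct skin contact and the reason for removing the blanket, but lists no burn or redness item.
- **Known harm.** Section 8.1.2 states: "Prolonged direct skin contact with the Ready-Heat blanket has been known to cause mild burns". It adds that some enrolled patients may be sedated.
- **Adverse event route.** Under section 8.1.1, events related to the study intervention, up to 24 hours, go on the eCRF with a CTCAE code. Section 8.2.4 uses CTCAE for severity, and section 8.2.5 has each diagnosed event categorised by CTCAE.

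**The concern.** Redness and a burn differ in clinical weight, and the protocol itself picks out burns as the harm to expect. A single count that merges the two cannot show which occurred. A count of occurrences also need not equal a count of patients, because one patient may contribute more than once.

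The pilot is meant to inform a definitive trial. For safety planning and consent in that trial, the useful quantity is the proportion of patients burned in each arm, with an upper confidence limit. If the pilot reports only the pooled count, readers cannot recover that quantity from the planned output. With about 30 to 37 patients per arm, information on an uncommon harm is already scarce, and pooling discards part of it.

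**Working it through.** **Inputs.** Section 7.1 gives 58 evaluable patients (29 per arm), inflated for 20% dropout to 74 (37 per arm). Section 5.1 gives 1:1 allocation. The documents state no expected burn rate, no acceptable limit and no precision target for safety.

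**Step 1: the plan's own figures.** The sample size rests on compliance, not burns. The exact probability that the sample proportion falls within 0.10 of 0.80 is 0.95529 at n = 57, which matches the table in section 7.1, and 0.95288 at n = 58. Inflation: 29 / (1 − 0.20) = 36.25, rounded up to 37 per arm, or 74 in total. Both reproduce, so 37 and 29 are the denominators used below.

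**Step 2: what the pooled count identifies.** Take an illustrative count of 5 in the intervention arm.

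- If the count means occurrences, 1 to 5 patients were affected, of whom 0 to 5 were burned.
- If the count means patients, 5 were affected, of whom 0 to 5 were burned.

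The range of burned patients is the same on either reading:

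| Denominator | Lowest | Highest |
|---|---|---|
| 37 | 0/37 = 0% | 5/37 = 13.5% |
| 29 | 0/29 = 0% | 5/29 = 17.2% |

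The summary cannot distinguish an arm with no burns from one in which more than an eighth of patients were burned.

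**Step 3: what a patient-level burn count would give.** With x burned patients out of n, the exact (Clopper-Pearson) 95% limits are beta quantiles. The lower is the 2.5% point of Beta(x, n − x + 1), and the upper is the 97.5% point of Beta(x + 1, n − x). For x = 0 the upper limit reduces to 1 − 0.025^(1/n):

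- n = 37: 1 − 0.025^(1/37) = 0.0949
- n = 29: 1 − 0.025^(1/29) = 0.1194

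| Patients burned | n = 37 | n = 29 |
|---|---|---|
| 0 | 0% (0 to 9.5%) | 0% (0 to 11.9%) |
| 1 | 2.7% (0.1 to 14.2%) | 3.4% (0.1 to 17.8%) |
| 3 | 8.1% (1.7 to 21.9%) | 10.3% (2.2 to 27.4%) |

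These intervals describe the precision available at this sample size. They do not measure the damage done by pooling, which is the loss of identification in Step 2.

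**The case against.** **The adverse event route already captures burns.** This is the strongest objection, and much of it stands. Related burns should appear individually on the eCRF with a CTCAE code and grade. Section 8.2.1 treats an event of uncertain cause as related, so a burn under the blanket is unlikely to be missed, and arm sizes are known. A reader might infer that the trial cannot state its burn rate. The documents do not support that, because a rate could be derived afterwards. Two gaps remain. Section 7.2 does not plan the derivation. Entry on the eCRF also depends on judged relatedness to the study intervention, and section 8.2.5 lets the investigator leave out events common in this population. Read literally, control-arm burns from other warming methods could go unrecorded there, which would weaken a comparison between arms.

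**The wording may mean patients, and the form may already split the two.** Either is possible, since the unit is loosely worded and the case report form is not in the documents. Step 2 shows that the patient reading does not remove the pooling. If the form already makes the split, only the outcome and table wording need to change.

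**Misuse of the count is hypothetical.** Agreed. The plan puts no binomial interval on the pooled count, and this point does not claim that it does.

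**Feasibility is a separate question.** A reader might infer that the trial would be called feasible at any level of harm, because none of the three rules in section 6.1 uses a skin result. That goes too far. Rule 2 concerns "Failure to apply and maintain the Ready-Heat® blanket in more than 20% of patients enrolled in the intervention arm" during trauma bay resuscitation, so burns that lead to early removal can count against it. Burns found later do not enter it. Reporting of serious events to the REB and sponsor runs separately. A burn limit among the feasibility rules is a design and clinical choice, and its absence contradicts nothing in the documents.

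**Conclusion.** The point holds as a gap in outcome definition and planned reporting. Outcome 16 and the section 7.2 summary, followed as written, do not give the proportion of patients burned, although burns are the device's named expected harm. In the example, a count of 5 leaves the burn proportion anywhere from 0% to 13.5% with 37 patients, or 0% to 17.2% with 29.

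This rests on two assumptions: that the summary is produced as section 7.2 words it, and that the Visit 3 item is not already divided on a form that cannot be seen here. The count of 5 is illustrative. The sample size is not in error on this point; it was set for compliance and gives only coarse precision for burns. The gap is worth closing before data collection, because events recorded without a split may be hard to reclassify later.

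**What to change.** 1. Redefine outcome 16 (section 3.6, and the matching item in the protocol summary) and the section 7.2 safety summary as the number of patients with (a) any burn, by CTCAE grade, and (b) redness only.
2. Report each by randomised arm, as a proportion with an exact 95% confidence interval. Event counts may be shown as well.
3. Record the Visit 3 skin item in the same split, for both arms, regardless of judged relatedness.

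**Cost.** A small change to data capture and table wording, with no change to the sample size. The intervals will be wide and should be presented as such.

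**Optional, outside this point.** The sponsor may wish to state whether a skin-safety result bears on the section 6.1 decision. No limit is proposed here.
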